10.0 STATISTICS

10.1 SAMPLE SIZE ESTIMATE

This study is a randomized open label multi-center Phase III adaptive trial using a group sequential design with a primary endpoint of overall survival (OS).

The study is designed to detect a 3.5 month increase in median OS from 10.7 months in the control arm to 14.2 months in the TheraSphere arm (i.e., hazard ratio = 0.754), using a log rank test.

A maximum of 417 deaths will yield 80% power to detect the target difference in median OS (ie, HR=0.754) with a two-sided alpha of 0.05 using a group sequential design with 2 interim analyses and stopping boundary defined by the rho family error spending function with rho=1.5 (Jennison and Turnbull, 2000)¹⁸. It is estimated that a maximum of 520 patients will need to be recruited over 60 months, with an 18 month additional follow-up period. This includes an adjustment to take account of an assumed 5% of patients who will be lost to follow-up and for whom a date of death is not recorded, and an assumed additional 5% of patients who will be erroneously randomized because they did not meet the eligibility criteria at randomization.

Sample size modification will be considered at the second interim analysis using the approach described in Mehta and Pocock (2011)¹⁶ which employs an un-weighted test statistic at the final analysis as recommended by Burman and Sonneson (2006)¹⁷. If the sample size is increased after the second interim analysis, the final analysis is planned when approximately, but no less than, 564 deaths have occurred, which will result in 80% power to detect an improvement in median OS from 10.7 to 13.7 months (ie, hazard ratio=0.781) using a log rank test with a final two-sided alpha of 0.0363. It is estimated that approximately 700 patients will need to be recruited over 66 months, with an 18 month additional follow-up period, in order to observe 564 deaths. This includes an adjustment to take account of an assumed 5% of patients who will be lost to follow-up and for whom a date of death is not recorded, and an assumed additional 5% of patients who will be erroneously randomized because they did not meet the eligibility criteria at randomization.

Sample size calculations were performed and verified with PROC SEQDESIGN, SAS 9.3.

[REDACTED]

[REDACTED]

[REDACTED]

10.2 STATISTICAL ANALYSIS PLAN

The statistical analysis plan will be written based on the final protocol and will be updated, as required, in association with any protocol amendments. The plan will include tables, listings and graphs and describe statistical programming considerations.

10.2.1 POPULATIONS AND SUB-GROUPS

▪ Modified Intent To Treat population (mITT)

A modified Intention To Treat (mITT) Population will be used to analyze all efficacy endpoints. This population is defined as randomized patients who met the study eligibility criteria at randomization. The analyses using this population will be performed according to the treatment group to which patients were randomized.

▪ Per Protocol Population (PP)

The PP population comprises patients in the mITT Population without major protocol deviations which may affect the efficacy evaluation. The analyses using this population will be performed according to the treatment actually received.

▪ Safety Analysis Population (SA)

All randomized patients who received study treatments at least once will be included in the safety analysis, and will be analyzed according to the treatment actually received.

- [REDACTED]

[REDACTED]

[REDACTED]

[REDACTED]

10.2.2 TRIAL ENDPOINTS

10.2.2.1 PRIMARY EFFICACY ENDPOINT

The primary study endpoint is OS which will be calculated as the interval between the randomization date and the date of death for any cause, with censoring at the date of last contact for patients alive at last contact.

10.2.2.2 SECONDARY STUDY ENDPOINTS

Time-to-progression will be compared between the Treatment and Control groups from time of randomization to radiological progression (including new liver lesions and extra-hepatic lesions) according to RECIST v 1.1 criteria by investigator determination.

Time-to-untreatable-progression will be compared between the Treatment and Control groups from randomization to radiological progression (including new liver lesions and extra-hepatic lesions) according to RECIST v 1.1 criteria by investigator determination. For patients randomized to the Treatment group, any liver lesion still amenable to TheraSphere treatment is not considered to be an untreatable progression. Untreatable progression will be defined as one of the following:

- Intolerance to sorafenib

- Occurrence of specific contraindications to sorafenib
- Assessment of progression in the target lesions or occurrence of new lesions after treatment and, for patients randomized to the treatment group, a maximum of 2 re-treatments with TheraSphere
- Occurrence of specific contraindications to TheraSphere and or appearance of lung/intestinal shunts or anatomical constraints not correctable by radiological procedures for the Treatment group.
- Confirmed extra-hepatic metastases
- Deterioration of liver function (Child Pugh score >B7)
- Clinical progression to ECOG performance status >1. Such deterioration in PS should be observed at two subsequent evaluations at 8 week intervals.

Time to symptomatic progression (TTSP): from the time of randomization to ECOG performance status >1 with or without tumor progression based on RECIST v1.1. Deterioration in performance status is to be confirmed at two subsequent evaluations at 8 week intervals.

Tumor Response according to RECIST v 1.1 criteria based on investigator assessment. At Baseline, target tumors are identified, read and measured for size. At all subsequent follow-up visits, the images (using the same modality) for the same target lesions will be read and measured and compared back to the Baseline images and then categorized according to the following table:

BEST RESPONSE	RECIST v 1.1
	Change in the sum of diameter of target lesions
CR	Disappearance of all target lesions
PR	≥30% decrease in the sum of diameters of target lesions
SD	Neither CR nor PR nor PD
PD	≥20% increase in the sum of the longest diameter of target lesions from the smallest value on study. The sum of diameters must also demonstrate an absolute increase of at least 5mm e.g. Two lesions increasing from 2mm to 3mm does not qualify.

Quality of Life Assessments: Functional Assessment of Cancer Therapy – Hepatobiliary Questionnaire – FACT-Hep. Patients will be asked to complete the questionnaire at Baseline and each of the 8 week study visits.

Safety will be assessed at all visits for enrolled patients using v 4.0 of the National Cancer Institute's Common Terminology for Adverse Events (NCI: CTAE). All adverse events, serious adverse events, and unanticipated adverse device effects as defined by the study protocol will be collected throughout the duration of the study. These events will be documented and recorded on the Adverse Event eCRF using the NCI Common Toxicity Criteria for Adverse Events; CTCAE v. 4.0 standards, and will be coded using the Medical Dictionary for Regulatory Activities (MedDRA).

10.2.3 EFFICACY ANALYSIS

The efficacy analyses will be performed on the mITT and PP populations.

10.2.3.1 PRIMARY ENDPOINT STATISTICAL ANALYSIS PLAN

Overall survival (OS) time will be calculated as the interval between the randomization date and the date of death for any cause, with censoring at the date of last contact for patients alive. The Kaplan-Meier method will be used to estimate the OS curves in the two treatment groups; comparison between the curves will be performed using the log-rank test.

Interim Analyses: Two interim analyses of OS are planned to be performed by the Independent Data Monitoring Committee (IDMC) based on group sequential stopping rules using an alpha boundary defined by the rho family error spending function with rho=1.5. The first interim analysis is planned at approximately, but no less than, 188 deaths, with a two-sided p-value ≤ 0.0151 allowing the study to be stopped early for efficacy. A second interim analysis is planned at approximately, but no less than, 250 deaths, with a two-sided p-value ≤ 0.0151 allowing the study to be stopped early for efficacy.

A conditional power of less than or equal to 15% at each of the interim analyses will result in the study stopping early for futility, using the method described in Proschan et al (2006)¹⁹.

Sample size modification will be considered at the second interim analysis using the approach described in Mehta and Pocock (2011)¹⁶.

[figure not shown]
Final Analysis: The final analysis, without a sample size modification, is planned when approximately, but no less than, 417 deaths have occurred. A two-sided p-value ≤ 0.0363 is required to declare a statistically significant improvement in median OS at the final analysis.

If the sample size is increased after the second interim analysis, the final analysis is planned when approximately, but no less than, 564 deaths have occurred, which will result in 80% power to detect an improvement in median OS from 10.7 to 13.7 months using a log rank test with a final two-sided alpha of 0.0363.

10.2.3.2 SECONDARY ENDPOINT STATISTICAL ANALYSIS PLAN

For secondary efficacy endpoints, each comparison between treatment groups will be conducted at $\alpha=0.05$ (two-sided). Secondary study endpoints will be analyzed only at the final analysis to determine the statistical significance, if any between, the Treatment and Control groups. Study-wise Type I error will be controlled using a sequential hierarchical approach, as shown in the figure below.

Hierarchical approach to control study-wise Type I error of primary and secondary efficacy endpoints

^a Type I error is controlled at $\alpha = 0.05$ (2-sided) over the 2 planned interim analyses and final analysis.

Further supportive analyses of the secondary efficacy time-to-event endpoints using the Cox regression model may be used to evaluate the effect of multiple covariates, including stratification factors.

- Time to progression (TTP) will be calculated as the interval between the randomization date and the date of first disease progression, including the appearance of new lesion(s) and death for any cause or of last contact for patients alive. The Kaplan-Meier method will be used to estimate the TTP curves in the two treatment groups; comparison between the curves will be performed using the log-rank test.

- Time to untreatable progression (TTUP) will be calculated as the interval between the randomization date and the first occurrence of one of the events listed in Section 0. The Kaplan-Meier method will be used to estimate the TTUP curves in the two treatment arms; comparison between the curves will be performed using the log-rank test.
- Time to symptomatic progression (TTSP) will be calculated as the time from randomization to ECOG performance status >1 with or without tumor progression (as defined in Section 0). The Kaplan-Meier method will be used to estimate the TTSP curves in the two treatment arms; comparison between the curves will be performed using the log-rank test.
- Tumor response rate. The response probability will be estimated in each of the two treatment groups as proportion of CR+PR (as defined in Section 0, tumor response according to RECIST v 1.1) over the total number of mITT or PP patients. The disease control rate (ie, CR+PR+SD) will also be compared between the treatment arms. Tumor response will be compared using the continuity adjusted Newcombe-Wilson test. The corresponding 95% confidence limits will be calculated.
- Quality of Life. The total score of FACT-Hep will be calculated, the scores of each domain and each question at each time-point and their differences from baseline will be summarized for each treatment group. The two treatment groups will be compared applying a mixed model repeated measures analysis with the treatment, visit and the interaction between treatment as factors, the baseline score as a covariate and further adjusted for the interaction between baseline and visit. A deterioration in QOL is defined as a 7-point decline in the total score or death whichever occurs first. The time to deterioration in QOL (TTDQoL) will be calculated as the interval between the randomization date and deterioration in QOL. The Kaplan-Meier method will be used to estimate the TTDQoL curves in the two treatment arms; comparison between the curves will be performed using the log-rank test

A detailed description of data censoring handling for patients will be defined in the Statistical Analysis Plan.

10.2.4 SAFETY ANALYSES

The safety analyses will be performed on the SA population.

All treatment emergent adverse events (TEAEs), defined as events which were not present at baseline or worsened in severity following the start of treatment, will be reported according to NCI Criteria. The incidence of TEAEs will be summarized according to MedDRA coded primary system-organ class (SOC) and preferred term (PT). The summaries will be presented overall (severity grades 1-5) and for grade ≥ 3 events and by treatment discontinuation. These summaries will present the number and percentage of patients reporting an adverse event for each classification level as well as the number of events reported.

Serious adverse events (SAEs) will be tabulated by treatment group.

Laboratory values will be summarized by treatment group over time and overall.

10.2.4.1 FEASIBILITY SAFETY ANALYSIS

After the first 20 patients in the Treatment group have received both TheraSphere and sorafenib treatment and completed at least 2 weeks of sorafenib therapy, a feasibility safety assessment will be conducted. The IDMC will review the safety results of both the Control and Treatment groups in an unblinded fashion.

The IDMC will take into consideration the established safety profiles of TheraSphere and sorafenib in this patient population as described in the product labelling, as well as the expected high rates of adverse events and death that are associated with disease progression in patients with intermediate to advanced HCC. The impact of disease progression in these patients may be understood by considering the placebo control data from the SHARP³ trial, as summarized in the SHARP trial publication and an EMEA¹⁴ overview of sorafenib including a safety review of the SHARP trial data.

A consideration for stopping further enrollment to trial may be made if there is

- An unanticipated patient death definitely or probably related to the sequential administration of TS followed by sorafenib, or
- there is a pattern of serious toxicity clearly related to the sequential administration of TS followed by sorafenib

as assessed by the IDMC experts based on the severity of disease of the enrolled population. Such a toxicity pattern must be clearly different from, or more severe than, what might be expected from independent administration of the products. The potential adverse impact of any such pattern of toxicity on the survival or well being of the patient should be considered in the context of the safety and outcome expectations of patients with advanced HCC.

10.2.5 POOLABILITY AND OTHER ANALYSES

The number of randomized patients, the number of patients treated, the number of patients in each analysis population will be summarized. The number of patients discontinuing from active treatments and reasons for discontinuation will be summarized. In the same manner the number of patients discontinuing follow up and reasons for discontinuations will be reported.

Listings of reasons for discontinuation from active treatments, from follow up, and reasons efficacy data cannot be evaluated in the PP population will be also provided.

Duration of follow up will be described by descriptive statistics such as median and interquartile range.

Demographic, patient and disease characteristics will be listed and summarized using appropriate descriptive statistics.

Multivariate Cox regression analysis of time-to-event efficacy endpoints will be conducted on stratification criteria and other factors such as age, gender, duration of disease prior to randomization to determine the impact of these factors on study endpoints.

As a sensitivity analysis, to address the poolability of data across regions, study sites and gender, a Cox regression analysis of the primary efficacy endpoint, OS, will be conducted with factors of region, study site and gender, and to determine the impact of these factors on OS. Note: region and study site will not be included simultaneously in the model due to collinearity.

Should the impact of region, site or gender on OS be statistically and clinically relevant, the reasons for the observed differential treatment effect, such as patient demographic or clinical characteristics, will be investigated and reported. If the poolability of OS results are in direct question as a result of this sensitivity analysis, the primary endpoint (OS) will also be analyzed separately by region, site or gender. In addition, the primary endpoint (OS) will be analyzed separately by US and non-US region. The specific

mechanism of merging low enrolling study sites into virtual sites for purposes of analysis will be detailed in the Statistical Analysis Plan.

An exploratory analysis will be performed to compare the tumor response rate, based on mRECIST criteria²⁰ and on a blinded centralized independent imaging assessment, between treatment arms using the continuity adjusted Newcombe-Wilson test.

10.2.6 INDEPENDENT DATA MONITORING COMMITTEE

An Independent Data Monitoring Committee (IDMC) will be established to oversee the conduct of the study, will follow the FDA's Guidance on IDMCs/DSMBs and comply with ISO 14155. The IDMC will meet periodically during the study to review enrollment, protocol deviations, and safety events for the study. In addition, the IDMC will conduct and review the feasibility safety analysis (per Section 10.2.4.1) and will evaluate the data at interim analyses for consideration of stopping the study for overwhelming efficacy or futility and for sample size re-estimation at the second interim analysis. The IDMC will make formal recommendations to the study Sponsor at the time of the feasibility safety analysis, at the time of the interim analyses, and during the conduct of the study based on detailed decision rules specified in the IDMC charter. An IDMC member or designate may act as the study independent medical monitor. The IDMC will evaluate the final study report.

11.0 DATA COLLECTION AND MANAGEMENT

11.1 ELECTRONIC DATA COLLECTION (EDC)

Data from this trial will be captured on electronic case reporting forms (eCRFs), and will be entered into a validated clinical database. An audit trail will be maintained to document all data changes in the database. Procedures will be followed to ensure the validity and accuracy of the clinical database.

The investigator will sign and date all indicated places on the eCRFs. This signature will indicate that thorough inspection of the data has been made and will certify that the Site Investigator has reviewed and approved the data contained on the forms.

11.2 DATA MANAGEMENT

The investigator will ensure that trial data quality is maintained to current standards of Good Clinical Practice and that data are submitted in a timely manner as outlined in the protocol and supporting documentation, including responses to data queries, until the trial is terminated. The investigator must sign an affirmation statement verifying the content of all subjects' eCRFs.

Errors must be corrected in accordance with EDC data entry guidelines.

12.0 ADVERSE EVENTS

Adverse experience will be considered synonymous with the term adverse event and vice versa.

12.1 ADVERSE EVENT DEFINITIONS

Adverse experience will be considered synonymous with the term adverse event and vice versa.

12.1.1 DEFINITIONS OF AE/SAE FOR DRUGS

Adverse Event (AE)

An AE is any untoward medical occurrence or undesirable event(s) experienced in a subject or clinical investigation subject that begins or worsens following administration of the study drug, whether or not considered related to the treatment by the investigator.

An undesirable event(s) can be, but is not limited to, symptoms experienced by a subject or objective findings, such as significant clinical laboratory abnormalities.

Serious Adverse Event (SAE)

Any untoward medical occurrence that at any dose:

- results in death;
- is life-threatening ("life-threatening" refers to an event in which the subject was at risk of death at the time of the event; it does not refer to an event which hypothetically might have caused death if it were more severe);
- requires inpatient hospitalization or prolongation of existing hospitalization;
- results in a persistent or significant disability/incapacity; or
- is a congenital anomaly/birth defect.

Medical and scientific judgment should be exercised in deciding whether medical events that may not be immediately life-threatening or result in death or hospitalization but may jeopardize the subject or may require intervention to prevent one of the other outcomes listed in the definition above, should also be considered serious.

12.1.2 DEFINITIONS OF ADE/SADE/UADE FOR DEVICES

Adverse Device Effect (ADE)

An adverse device effect is an adverse event (AE – previously defined) related to a medical device and includes any event resulting from insufficiencies or inadequacies in the instructions for use or the deployment, implantation, installation or malfunction of the device; any event that is the result of user error; or any potential adverse device effect which might have occurred if suitable action had not been taken or intervention had not been made or if circumstances had been less fortunate.

Serious Adverse Device Effect (SADE)

A Serious Adverse Device Effect is an adverse device effect that has resulted in any of the consequences characteristic of a serious adverse event (SAE – previously defined) or might have led to any of these consequences if suitable action had not been taken; intervention had not been made or circumstances had been less fortunate.

Unanticipated Adverse Device Event (UADE)

An unanticipated adverse device effect is any serious adverse effect which by its nature, incidence, severity and outcome has not been identified in the risk assessment, the informed consent form as well as the protocol.

12.2 RECORDING ADVERSE EVENTS

All adverse events and adverse device effects will be documented from the date of randomization until study exit. For patients who permanently discontinue sorafenib in either arm of the study, AEs will be documented for 30 days from the date of discontinuation. After this period, only AEs considered to be related to TheraSphere will be collected.

In this study, patients should be encouraged to report adverse events spontaneously or in response to general, non-directed questions. At any time during the study, the patient may volunteer information that resembles an adverse event. Once it is determined that an adverse event has occurred, the Investigator should obtain all the information required to complete the adverse event form. Any medical management of an event and the date of resolution of the event must be recorded in the source document and on the appropriate case reports form(s) using medical terminology according to sponsor instructions.

For each AE, the following information will be recorded:

- Adverse event
- Serious/non-Serious
- Severity (Toxicity Grade)
- Action taken
- Relationship to study treatment
- Expected/Unexpected
- Date and time of onset
- Date and time of resolution

An expected adverse event is any AE, the nature or severity of which is identified in the relevant Package Insert.

Any AE experienced by a subject will be followed until the AE has resolved to the investigator's or physician sub-investigator's satisfaction. If a problem still exists, then the investigator or physician sub-investigator at his/her discretion will ask the subject to come back to the clinic for further evaluation. Any serious adverse events should be managed as discussed in Section 12.3.

Once the subject has been discharged from the study, the investigator has no obligation to seek further follow-up with the subject in order to identify new AEs. However, if the investigator becomes aware of an SAE that has occurred following the subject's discharge from the study and the investigator considers the SAE possibly, probably, or definitely related to a study drug or device, then the investigator should report the SAE as described in the protocol.

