At the International Liver Cancer Association conference in September 2010, Metrakos⁹ et al reported preliminary results of a Phase II investigation of the safety, tolerability and efficacy of administering TheraSphere and Nexavar (sorafenib) treatment in patients with HCC. In this trial, all patients (N=26) began sorafenib 400 mg BID at least 7 weeks in advance of TheraSphere treatment which was administered in a sorafenib window. Most patients (65%) required sorafenib dosage adjustment. The most common toxicities were diarrhea, fatigue and hand foot syndrome with most being self-limiting and responsive to dose adjustment. One single grade 4 toxicity of worsening cirrhosis was observed. Median survival is 15.5 months which exceeds that reported in the sorafenib or placebo arms of the SHARP study (10.7 and 7.9 months respectively). The reported toxicities are consistent with the toxicity profile of both TheraSphere and sorafenib with no apparent increase in severity or frequency.

As illustrated by these published reports, there is now an extensive clinical experience demonstrating the safety of TheraSphere in the management of patients with unresectable HCC.

[figure not shown]
The early reports of serious adverse events possibly associated with the use of TheraSphere included death, hepatorenal failure, liver abscess, hepatic encephalopathy, hepatic decompensation, radiation hepatitis, radiation pneumonitis, duodenal ulcer, gastrointestinal bleeding and cholecystitis. As clinical experience with TheraSphere increased, the pre-treatment high risk factors associated with these early serious events were identified, leading to improved patient selection criteria and thereby lowering the risk of these events occurring. These risk factors include infiltrative tumor type, bulk disease (tumor volume >70% or nodules

too numerous to count), AST or ALT > five times the upper limit of normal, bilirubin > 2 mg/dL, tumor volume >50% in the presence of an albumin < 3 g/dL and those in whom extra-hepatic shunting to the lungs or gastrointestinal tract cannot be managed through standard angiographic techniques.

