12.3 SUBMITTING EXPEDITED SAFETY REPORTS

Any SADE or UADE (defined previously) must be reported by telephone or fax to the sponsor or designate as specified in the study procedures within 24 hours of learning of the event. In the event of an emergency, the Investigator will contact the CRO using the coordinates specified in the study procedures.

The SAE form provided by the sponsor should be completed and signed by the investigator or physician sub-investigator. The entire SAE form needs to be completed, if possible, to keep requests for additional information to a minimum. **Patients experiencing SAE, SADE or UADE should be followed clinically and with laboratory studies, if appropriate, until medical treatment and/or medical monitoring of the event is no longer required because the event resolves or stabilizes, returns to baseline if a baseline value is available, can be attributed to agents other than the study treatments or a referral for appropriate follow-up care has been made.**

The Investigator must promptly inform the IRB of all unexpected SAE or UADE. These events will be reported by the sponsor or its designate as appropriate to the regulatory authorities according to relevant jurisdictional medical device regulations. The Investigator will receive notification of these events across all study centers from the sponsor.

Each AE reported on an SAE form must also be reported in the adverse event section of the eCRF.

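### Protocol 12.2 lets a listed event type count as expected at any severity, and the UADE definition in 12.1.2 is ambiguous, so a worse-than-listed event may not trigger prompt reporting under 12.3

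*Protocol*

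**What the plan says.** Protocol 12.2 has sites record, for each adverse event, whether it was expected or unexpected, and gives one definition: "An expected adverse event is any AE, the nature or severity of which is identified in the relevant Package Insert". *Unexpected* is not defined separately, so it has to be read as the complement. Frequency and outcome do not enter.

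Protocol 12.1.2 limits the UADE label to serious effects and sets this condition: "which by its nature, incidence, severity and outcome has not been identified in the risk assessment, the informed consent form as well as the protocol". The reference documents are therefore not those of 12.2, which names only the package insert.

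Protocol 12.3 attaches actions to the two labels: "The Investigator must promptly inform the IRB of all unexpected SAE or UADE". It continues: "These events will be reported by the sponsor or its designate as appropriate to the regulatory authorities according to relevant jurisdictional medical device regulations". Investigators at all centers are then notified of the same events by the sponsor. A separate route in 12.3 does not depend on expectedness: "Any SADE or UADE (defined previously) must be reported by telephone or fax to the sponsor or designate", within 24 hours of the site learning of the event.

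**The concern.** An expectedness rule should separate events that behave as the reference document says from those that do not. Joining nature and severity with *or* defeats this for severity: once an event type is in the insert, no grade makes it unexpected.

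This matters in a trial of two treatments given in sequence. Protocol 9.2.15.1 names additive or synergistic adverse events as the risk to be minimized, and 12.2.1 notes that the two safety profiles share many similar events. A plausible harm is therefore a familiar event in a worse form, which is the case that the wording of 12.2 classes as expected. What is at stake is whether the IRB, regulators and the other centers hear of it promptly under the protocol's own rule. With up to 105 centers, an ambiguous definition will also be applied unevenly.

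**Working it through.** The documents give no figure for this point, so the check sets out the logical cases. The counts are numbers of combinations, not probabilities.

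**Expectedness (12.2).** Two attributes, each identified in the package insert or not: 2 × 2 = 4 combinations.

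| Nature listed | Severity listed | As written (*or*) | If both required (*and*) |
|---|---|---|---|
| yes | yes | expected | expected |
| yes | no | expected | unexpected |
| no | yes | expected | unexpected |
| no | no | unexpected | unexpected |

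As written, 3 of 4 are expected; with *and*, 1 of 4. For an event of listed nature, the present wording makes 0 of 2 severity states unexpected; the alternative makes 1 of 2 unexpected, the one whose severity is not listed.

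**UADE (12.1.2).** Four attributes, each identified or not: 2^4 = 16 combinations. The sentence supports two readings:

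- Reading A: all four attributes must be unidentified. Then 1 of 16 combinations qualifies.
- Reading B: the effect, as characterized by the four together, is not identified, so one departure is enough. Then 16 − 1 = 15 of 16 qualify.

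If the nature is already identified, 2^3 = 8 states of incidence, severity and outcome remain. Reading A admits 0 of 8; reading B admits 8 − 1 = 7 of 8.

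**The chain to 12.3.** Take a serious event of listed nature and greater severity than listed.

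1. Related to TheraSphere: 12.2 makes it expected. Under reading A it is not a UADE either, so the trigger in 12.3 does not fire. Under reading B it is a UADE, and the trigger fires.
2. Attributed to sorafenib only: it is not a device effect, so 12.1.2 does not apply and 12.2 alone decides. Read literally, it is expected. Section 12.2.1 confines expedited reporting to events attributed to TheraSphere, so the step most clearly at issue here is the prompt IRB notice.

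No other section of the protocol corrects either definition.

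**The case against.** The best reply is that the protocol does not rely on this label alone. Every serious device effect reaches the sponsor within 24 hours whatever its expectedness (12.3). Serious events go to the IRB under local procedures with no expectedness filter (13.3). Regulator reporting follows device regulations (12.3), investigators have further duties under 21 CFR 812.150 and ISO 14155 (13.10), and 13.6 holds the sponsor to the most protective applicable standard. The IDMC reviews safety periodically (10.2.6), and periodic safety reports go to all centers (12.4). This stands as mitigation, and a claim that such events simply escape the IRB and regulators would be wrong. It does not close the gap: none of these routes changes the definition that sites apply, 13.3 sets no uniform prompt requirement, and the 24-hour route covers only TheraSphere-related events.

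Three stronger readings may tempt a reader and are not supported.

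- *That a known event can never be unexpected or a UADE.* This needs reading A of 12.1.2, and reading B is equally open.
- *That every serious event named in 5.3 or listed in 12.5.1 is automatically expected.* Those lists are protocol text. They bear on the UADE test, but the reference in 12.2 is the package insert, which is appended and not reproduced in the text reviewed.
- *That 12.2 contradicts the stopping language in 10.2.4.1, or makes its unanticipated-death trigger almost unreachable.* That section is a separate criterion applied by the IDMC to accumated data. It does not adopt the 12.1.2 definition, and it has a second trigger based on a pattern of toxicity: "Such a toxicity pattern must be clearly different from, or more severe than, what might be expected from independent administration of the products". That trigger does not depend on how sites code expectedness.

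**Conclusion.** The defect in 12.2 is real on the plain wording: severity beyond what is listed cannot make a listed event type unexpected. The point about 12.1.2 is ambiguity, not a demonstrated error. Together they mean that a known event more severe than listed **may** fail to trigger the prompt-reporting rule in 12.3.

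The conclusion assumes that sites apply 12.2 literally and that *unexpected* means not expected as there defined; for device effects it also assumes reading A of 12.1.2. The number of events affected cannot be given, because the documents report no expectedness data and the package inserts are not reproduced.

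This is a safety-reporting matter worth correcting. It does not touch sample size, power or type I error, and none of the adverse event summaries in SAP 8.7.2 uses expectedness.

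**What to change.** - **Protocol 12.2:** define an expected event as one whose nature **and** severity are both consistent with the relevant package insert, and state that an event of listed nature but greater severity than listed is unexpected.
- **Protocol 12.1.2:** state that a UADE is a serious effect whose nature, incidence, severity **or** outcome has not been identified.
- **Both definitions:** reconcile the reference documents, so that sites know which source governs each label.

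The cost is a wording change to two definitions, a note to sites, and somewhat more IRB and regulator reports. Since 12.2 already has seriousness, toxicity grade and expectedness recorded for each event, serious events previously marked as expected could be re-screened against the revised wording without new data collection.
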